10.1.2 Secondary Endpoints

AKI Secondary Endpoints:

- Incidence of AKI stage ≥ 2 (by AKIN SCr criteria) following an i.v. injection of iodinated iso-osmolar contrast material iodixanol (VisipaqueTM Injection 320 mgI/mL) or saline in patients with CKD stage III/IV assessed at 48 hours post-baseline (Follow-up 1).
- Incidence of AKI (by standard definition of CIN [[Mehran and Nikolsky 2006](#)]) following an i.v. injection of iodinated iso-osmolar contrast material iodixanol (VisipaqueTM Injection 320 mgI/mL) or saline in patients with CKD stage III/IV assessed at 48 hours post-baseline (Follow-up 1).
- Incidence of AKI stage ≥ 2 (by Waikar criteria [[Waikar and Bonventre 2009](#)]) following i.v. administration of iodinated iso-osmolar contrast material iodixanol (VisipaqueTM Injection 320 mgI/mL) or saline in patients with CKD stage III/IV assessed at 48 hours post-baseline (Follow-up 1).

Other Secondary Endpoints:

- Mortality and morbidity (i.e. critical events, including EVAR-related post-baseline events, as adjudicated by the CEAC) assessed at 6 months (Follow-up 3) in patients with CKD stage III/IV.
- Blinded independent assessment of image quality/diagnostic confidence using a 5-point scale.

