12.1 General Statistical Considerations

Tabulations of summary statistics, graphical presentations, and statistical analyses will be performed with SAS® software, Version 9.2 or higher. Descriptive statistics for continuous data in summary tables will include the number of patients in the analysis (n), mean, standard deviation, median, and range (minimum, maximum). Descriptive statistics for categorical data in summary tables will include counts and percentages. The last observation prior to administration of Visipaque™ or saline placebo will be used as the baseline value for calculating changes from baseline after administration of Visipaque™ or saline placebo. All data obtained on the eCRF and entered into the database will be provided in separate data listings showing individual patient values. All summary tables and data listings will be separated by treatment groups. Statistical tests will use a 0.05 significance level for 2-sided tests and 0.025 for 1-sided tests. The planning and reporting of statistical analysis will be carried out as described in the Sponsor/CRO's SOPs governing clinical studies.

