12.7 Secondary Analyses

12.7.1 Secondary Variables and Analyses

The secondary hypothesis to be tested for the secondary endpoints that are proportions is the following:

$$H_0: P_1 - P_2 \geq 0.05$$

$$H_1: P_1 - P_2 < 0.05$$

The secondary hypotheses will be tested in patients in the FAS with CKD stage III and IV combined. The incidences for the 2 treatment groups (CECT vs NECT) will be compared by using the same statistical method as for the primary analysis.

AKI Secondary Endpoint Analyses:

The secondary endpoints of the study are:

Incidence of AKI stage ≥ 2 (by AKIN SCr criteria [\[AKIN 2015\]](#)[\[Mehta et al. 2007\]](#)) following an i.v. injection of iodinated iso-osmolar contrast material iodixanol (Visipaque™ Injection 320 mg I/mL) or saline in patients with CKD stage III or IV. This analysis will be performed for the FAS assessed at 48 hours post-baseline (Follow-up 1).

Incidence of AKI (by standard definition of CIN [[Mehran and Nikolsky 2006](#)]) following an i.v. injection of iodinated iso-osmolar contrast material iodixanol (VisipaqueTM Injection 320 mg I/mL) or saline in patients with CKD stage III or IV. This analysis will be performed for the FAS assessed at 48 hours post-baseline (Follow-up 1).

Incidence of AKI stage ≥ 2 (by Waikar criteria [[Waikar and Bonventre 2009](#)]) following i.v. administration of iodinated iso-osmolar contrast material iodixanol (VisipaqueTM Injection 320 mg I/mL) or saline in patients with CKD stage III or IV. This analysis will be performed for the FAS assessed at 48 hours post-baseline (Follow-up 1).

In order to control the false positive rate at a one-sided 0.025 level across the testing of the secondary endpoints, the above endpoints will be tested hierarchically in the order given above. Each endpoint will be tested at a one-sided 0.025 level of significance; when a statistical test for a given endpoint fails to reach statistical significance in the appropriate direction, testing on all remaining secondary endpoints in the hierarchy will cease and the study will be considered successful on all secondary endpoints up to that point.

Secondary endpoint analyses will be repeated in the FAS for CKD stage III and IV separately and in the PP set by CKD stage and for stage III/IV combined.

Other Secondary Endpoint Analyses:

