Other secondary endpoint analyses will be conducted using the safety population for stage III/IV combined. In addition, these summaries and analyses will be repeated for the stage III CKD subgroup and the stage IV CKD subgroup separately.

Mortality and morbidity events:

- All-cause death assessed at 6 months (Follow-up 3).
- Critical events (including EVAR-related post-baseline events as adjudicated by the CEAC) assessed at 6 months (Follow-up 3).
- Incidence rate of hospitalization due to renal failure assessed at 6 months (Follow-up 3).
- Incidence of requirement for renal replacement therapy (i.e., renal transplant, dialysis, or hemofiltration/ultrafiltration) assessed at 6 months (Follow-up 3).
- Incidence of the composite of death and hospitalization events due to renal failure assessed at 6 months (Follow-up 3).
- Hospital length of stay (LOS) in days assessed at 6 months (Follow-up 3).
- Incidence rate of patients with $\geq 30\%$ reduction in eGFR at 48 hours compared to baseline.
- Other criteria defined by the CEAC.

Among the morbidity and mortality events, binary variables will be analyzed using the noninferiority test for proportions described above. Hospital LOS will be summarized descriptively by arm.

[figure not shown]
Image quality/diagnostic confidence analyses:

- Image quality/diagnostic confidence will be rated on a scale of 1 to 5. The frequency distribution of image-quality/diagnostic confidence ratings will be summarized for each type of imaging procedure in each treatment arm. Thus, there will be 2 separate summaries of image quality/diagnostic confidence ratings, CECT and NECT plus non-contrast duplex ultrasonography images. Both by-reader and majority-read analyses will be performed for each summarization.
- The image-quality/diagnostic confidence ratings will be analyzed based on individual scores and will also be dichotomized as evaluable (rating of 3 to 5) or nonevaluable (rating of 1 or 2). The frequency distribution of evaluable vs nonevaluable image quality/diagnostic confidence ratings will be summarized for each treatment group. Thus, there will be 2 separate summaries of image quality/diagnostic confidence ratings: CECT and NECT plus non-contrast duplex ultrasonography. Both by-reader and majority-read analyses will be performed for each summarization.

No statistical comparisons between the CECT images and NECT images plus duplex ultrasonography images will be made.

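### The one-sided 0.025 control in 12.7.1 and the synopsis covers only the three AKI secondary endpoints; the mortality and morbidity noninferiority tests lie outside it and should be labelled nominal

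*Combined protocol and SAP*

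**What the plan says.** Section 10.1.2 puts two groups under its Secondary Endpoints heading. The first is the three AKI endpoints at 48 hours: AKIN stage 2 or higher, the standard CIN definition, and Waikar stage 2 or higher. The second, headed as other secondary endpoints, includes "Mortality and morbidity (i.e. critical events, including EVAR-related post-baseline events, as adjudicated by the CEAC) assessed at 6 months".

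Section 12.7.1 opens with one noninferiority hypothesis, margin 0.05, for the secondary endpoints that are proportions. Under its AKI heading it gives the aim, "In order to control the false positive rate at a one-sided 0.025 level across the testing of the secondary endpoints", and the means: "the above endpoints will be tested hierarchically in the order given above". It adds: "Each endpoint will be tested at a one-sided 0.025 level of significance". The endpoints above that sentence are the three AKI definitions.

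The part of 12.7.1 on other secondary endpoints lists six binary mortality and morbidity items: all-cause death, critical events, hospitalization for renal failure, renal replacement therapy, the composite of death and renal hospitalization, and an eGFR fall of at least 30% at 48 hours. Hospital length of stay is also listed, and the list ends with "Other criteria defined by the CEAC". Of these, "binary variables will be analyzed using the noninferiority test for proportions described above", and "these summaries and analyses will be repeated for the stage III CKD subgroup and the stage IV CKD subgroup separately". The synopsis has the same structure. Section 12.1 fixes the level for every test: "Statistical tests will use a 0.05 significance level for 2-sided tests and 0.025 for 1-sided tests".

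**The concern.** The control sentence speaks of the secondary endpoints, and 10.1.2 counts mortality and morbidity among them, but the only control device is a sequence of three AKI tests. The other binary endpoints receive the same formal test with no order, gate or division of alpha. They are not marked as descriptive either. The plan does mark items that way when it means to: length of stay is to be summarized descriptively, and no statistical comparison is to be made for image quality.

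At stake is what the report may claim. Section 5 makes demonstrating safety through 6-month mortality and morbidity a secondary objective, and 12.6.2 says that noninferiority is concluded when the upper 95% limit is below 5%. A noninferiority statement on death or dialysis could then appear beside a 2.5% control statement that does not cover it.

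**Working it through.** **1. The plan's own test.** Inputs from 12.8: 10% in both arms, margin 5 points, one-sided 0.025, power 80%, Miettinen-Nurminen score test, 582 per arm. With restricted estimates of 0.1303 and 0.0803 under the null, n per arm = ((1.960·√(0.1303·0.8697 + 0.0803·0.9197) + 0.842·√0.18) / 0.05)² = 580.7, or 581. Exact power at 582 per arm is 80.5%, so the stated 582 is reproduced.

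**2. Error of a single test.** Exact type I error of this test at 582 per arm, with the true difference at the margin:

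| Control rate (assumed) | Type I error |
|---|---|
| 1% | 2.23% |
| 2% | 2.29% |
| 5% | 2.41% |
| 10% | 2.47% |

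Each test on its own is sound. The question is only how many are run.

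**3. The hierarchy.** Fixed-order testing of the three AKI endpoints at 0.025, stopping at the first failure, keeps the chance of any false result among those three at or below 2.5%. For them the stated control holds.

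**4. Tests outside the hierarchy.** For k independent endpoints all truly at the margin, the chance of at least one false noninferiority result is 1 − 0.975^k:

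- k = 2: 4.9%
- k = 3: 7.3%
- k = 6: 14.1%

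With the exact sizes from step 2, two independent endpoints give from 1 − (1 − 0.0223)² = 4.4% to 1 − (1 − 0.0247)² = 4.9%.

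**5. Why six independent endpoints cannot occur.** The composite contains death and renal hospitalization. Critical events, as listed in 10.2.5, contain death, renal replacement therapy and renal hospitalization. If death and renal hospitalization each carried a separate 5-point excess, the composite's excess would be about 10 points, not 5. The 14.1% is therefore a ceiling.

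**6. Correlated statistics.** Equally correlated normal statistics, all at the margin (illustrative, since step 5 limits how far this can be true):

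| Correlation | Six outside tests | Seven statistics |
|---|---|---|
| 0.3 | 12.2% | 13.8% |
| 0.5 | 10.4% | 11.4% |
| 0.7 | 8.3% | 8.9% |
| 0.9 | 5.4% | 5.8% |

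**7. Nested binary data.** 582 per arm. Assumed control rates: death 3%, renal hospitalization 2%, renal replacement 1%, eGFR fall 3%, AKIN stage 2 or higher 1%. Each is 5 points higher with contrast. Death and renal hospitalization are disjoint and form the composite, which is then 10 points worse; the other endpoints are independent, and critical events are left out. At least one false result occurs in 9.0% of simulated trials for the five outside tests, and in 11.1% when the first AKI test is added. The composite contributes nothing.

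The stage III and stage IV repeats are not counted in any of these figures. They add further tests at the same level.

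**The case against.** The strongest reply is about scope. The control sentence stands under the AKI heading, follows a list of three endpoints introduced as the study's secondary endpoints, and applies its stopping rule to endpoints in the hierarchy. The secondary hypotheses are placed in the FAS, whereas mortality and morbidity use the safety population and are grouped with safety outcomes. On that reading the sentence is true. This stands for the three AKI endpoints, so a reader should not infer that the stated control fails outright. It does not settle the matter, because 10.1.2 and the 12.7.1 subheading both call mortality and morbidity secondary, the hypothesis is stated for secondary proportions generally, and the tests carry no nominal label.

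On size, a false noninferiority result requires an endpoint that is truly at least 5 points worse. If none is, none can occur, so 2.5% is not a floor. This stands.

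A reader might infer that the list can be extended at will. The documents do not support that. Section 9.7 has the CEAC appointed before enrolment, working blinded under a charter that lists the critical events. The charter is not among the documents, so whether the list is closed cannot be told, and only binary additions would be tested. Equally, nothing in 12.7.1 closes it.

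Multiplicity matters little if the arms are equal. At an assumed 2% in both arms, the chance of passing is 99.98% at 0.025 and 99.6% at 0.025/7 = 0.0036. It matters more under modest harm: at 2% versus 4% it falls from 79% to 49%. For rare events the reused 5-point margin makes passing easy in any case, which is a separate question.

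Finally, a separate SAP might add an adjustment. The protocol defers to it on missing data, exclusions and sample size re-estimation, but not on multiplicity, and the supplied text contains no such adjustment.

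**Conclusion.** Wrong as written, in a limited sense. The one-sided 0.025 control holds for the three AKI endpoints and does not extend to all the secondary endpoints of 10.1.2. If two or more of the mortality and morbidity endpoints were truly at the 5-point margin, the chance of at least one false noninferiority result would exceed 2.5%: 4.9% for two independent endpoints, and roughly 6% to 11% in the nested scenarios and the seven-statistic scenarios with correlation 0.5 to 0.9. These figures rest on assumed event rates and correlations, because the plan gives none for these endpoints, and on 582 analysed per arm. A reader might take 14.1% as the plan's error rate; the overlap between endpoints rules that out. The primary analysis is unaffected.

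**What to change.** In 12.7.1 and the synopsis, reword the control sentence so that the 0.025 level applies across the three AKI secondary endpoints. In the same places, state that the mortality and morbidity analyses, including CEAC-defined criteria and the CKD-stage repeats, are nominal: between-arm differences with 95% CIs, without multiplicity control and without a confirmatory noninferiority claim. Align the mortality and morbidity objective in section 5, and check that the general hypothesis opening 12.7.1 does not reinstate the claim.

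The prespecified calculations need not be removed; a label is enough. No data or patients are affected. The cost is a few sentences in three places, and the sponsor gives up presenting the 6-month results as confirmatory noninferiority findings.

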9.9 Image Interpretation

CT and ultrasound images will be read at the site according to usual clinical practice to facilitate patient management decisions.

Images will also be read in a central independent blinded read in order to assess image quality/diagnostic confidence.

Images will be read by a panel of independent blinded readers appropriately qualified in abdominal imaging. Each CECT (CTA) image or NECT image plus duplex ultrasonography image will be read by 3 independent readers who will be randomly selected from the panel.

Detailed reader selection criteria will be provided in the Independent Read Charter. Readers will be provided with a Reader Training Manual for CECT and NECT plus Ultrasound assessments. This manual will provide the detailed assessment criteria which will include, but are not limited to, the diagnosis of the following items with regard to their confidence in making patient management decisions: i.e., status of the graft, stenosis, aneurysm rupture, endoleaks. A 5-point scale will be used to rate the visual assessment of image quality/diagnostic confidence:

5= excellent image quality, highest confidence for use in treatment decisions

4= good image quality, good confidence for use in treatment decisions

3= sufficient image quality, moderate confidence for use in treatment decisions

2= restricted image quality, low confidence for use in treatment decisions

1= poor image quality, no confidence for use in treatment decisions

A rating of 1 or 2 equates to the images being considered non-diagnostic. If a reader gives a 1 or 2 rating, the reader will be required to enter the reason for that rating in a freeform text entry field.

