For a randomly selected subset of 5% of the patients (N=29 in each arm), the images will undergo a second blinded visual assessment by the same reader. Intra-reader (within-reader) agreement for these blinded visual image assessments will be measured by percentage agreement. A percentage agreement with an exact 95% CI will be determined for each reader comparison and all readers for subjects with re-reads of images. In cases where images are re-read, it is the result of the first read that is to be included in the image quality/diagnostic confidence summaries.

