12.8 Sample Size Calculation

The primary endpoint is the incidence rate (proportion) of AKI stage ≥ 1 (by AKIN SCr criteria) at 48 hours after intervention in patients with stage III or stage IV CKD. With P1 defined as the incidence rate of AKI stage ≥ 1 following i.v. administration of Visipaque™ and P2 defined as the incidence rate of AKI stage ≥ 1 following administration of saline placebo, the sample size estimate is based on the following assumptions and statistical method:

- (1) Both P1 and P2 are 10%
- (2) A noninferiority margin of 5%
- (3) Power of 80% using the 95% CI of P1 – P2
- (4) The score test [Miettinen and Nurminen 1985] with a 1-sided 0.025 significance level is employed

A sample size of 1164 randomized patients (582 per treatment group) in the FAS will provide 80% power to demonstrate noninferiority of the proportion of AKI stage ≥ 1 (by AKIN criteria) in patients receiving Visipaque™ Injection 320 mgI/mL as compared with patients receiving the saline placebo.

To compensate for a screen failure rate of approximately 15%, approximately 1370 patients will be screened.

It is expected that the number of patients who are excluded from the PP set will be small, resulting in minimal loss of statistical power. However, the number of patients excluded from

the PP set will be monitored and the sample size may be increased as needed to maintain adequate statistical power to repeat the primary analysis in the PP set.

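### If more than one reader re-reads each selected patient, the exact 95% CI for intra-reader agreement pooled over readers ignores within-patient correlation and is too narrow; the plan does not say how many re-read

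*Combined protocol and SAP*

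**What the plan says.** Section 9.9 provides that each image set "will be read by 3 independent readers who will be randomly selected from the panel". The size of the panel is not given.

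Section 12.7.1, repeated in the synopsis, takes a 5% sample of patients, 29 per arm, for the re-read. Of this sample it says that "the images will undergo a second blinded visual assessment by the same reader". The measure is simple: "Intra-reader (within-reader) agreement for these blinded visual image assessments will be measured by percentage agreement". The interval is then specified for two levels of summary: "A percentage agreement with an exact 95% CI will be determined for each reader comparison and all readers for subjects with re-reads of images".

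Three things are not stated: whether one, two or all three first readers re-read a selected patient, what the denominator of the pooled figure is, and whether any allowance is made for repeated patients or readers. Section 12.7.1 also says that only the first read enters the image-quality summaries and that the two imaging strategies are not compared statistically.

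**The concern.** An exact binomial interval is valid when the pairs (first read against re-read) are independent. For a single reader, each patient supplies one pair, so repeated patients do not arise. In the pooled figure they can. If all three first readers repeat their own reads, each patient supplies three pairs on the same images. A clear image tends to be scored the same way twice by everyone and a borderline one less so, so positive correlation within a patient is plausible. The effective number of observations is then smaller than the number of pairs.

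What is at stake is the stated precision of one reliability figure. It supports a named secondary endpoint, image quality and diagnostic confidence, and it is the only reproducibility measure given for that endpoint in the text available. A reader of the study report also could not tell whether the pooled interval rests on 58 or 174 pairs.

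**Working it through.** **The plan's own figure.** The 5% is taken from 582 patients per arm (Section 12.8: "A sample size of 1164 randomized patients (582 per treatment group) in the FAS will provide 80% power"). 0.05 × 582 = 29.1, so 29 per arm and 58 in total. This reproduces.

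**Inputs.**
- From the documents: 29 re-read patients per arm; three first readers per patient; exact 95% CI.
- Assumed, because the documents give no value: m = 3 re-reads per patient (m = 1 as the alternative); agreement of 80% (90% as a check); ICC from 0.1 to 0.5.

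**Width.** Pairs = 58 × 3 = 174. Design effect = 1 + (m − 1) × ICC = 1 + 2 × ICC. Effective n = 174 / design effect. The adjusted interval is Clopper-Pearson at the effective n. At 80% agreement, both arms pooled:

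| ICC | Design effect | Effective n | 95% CI | Width relative to unadjusted |
|---|---|---|---|---|
| 0 (as planned) | 1.0 | 174 | 73.3% to 85.7% | 1.00 |
| 0.1 | 1.2 | 145 | 72.6% to 86.2% | 1.10 |
| 0.2 | 1.4 | 124 | 71.9% to 86.6% | 1.19 |
| 0.3 | 1.6 | 109 | 71.2% to 87.1% | 1.28 |
| 0.5 | 2.0 | 87 | 70.1% to 87.8% | 1.43 |

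Measured against the correct half-width, the planned one is short by 1 − 1/√(1 + 2 × ICC): 9% at ICC 0.1 and 29% at ICC 0.5.

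**Coverage.** Patient-level agreement probabilities were drawn from a beta distribution with the stated mean and ICC, pairs were drawn binomially within patient, and the unadjusted Clopper-Pearson interval was applied to the total (40,000 replicates; Monte Carlo standard error at most about 0.2 points).

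| ICC | 58 × 3, 80% agreement | 58 × 3, 90% agreement | 29 × 3 (by arm), 80% agreement |
|---|---|---|---|
| 0.1 | 93.2% | 95.0% | about 95% |
| 0.2 | 90.6% | 93.2% | about 93% |
| 0.3 | 88.6% | 91.2% | about 91% |
| 0.5 | 83.7% | 87.2% | about 87% |

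**One re-read per patient.** With m = 1 the design effect is 1 whatever the ICC. Both arms pooled give n = 58 and, at 80% agreement, an exact interval of 67.4% to 89.4%. Simulated coverage is 96.8% to 97.4% at every ICC tried, so the planned interval is slightly conservative.

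**The case against.** A reader might infer that the plan pools 174 pairs from 58 patients and that its interval is therefore wrong. The documents do not support that. Section 12.7.1 speaks of the same reader in the singular. No passage says that all three readers re-read, and with one re-read per patient the within-patient problem is absent. The counter-argument is that with three first readers the phrase most naturally means that each repeats his or her own read, since no rule is given for choosing one of the three. That is reasonable, but it remains an inference.

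The 174 is also uncertain on a second count. Section 12.1 has all summary tables separated by treatment group, so a by-arm figure on at most 87 pairs is at least as natural. On that layout ICC 0.1 produces no shortfall, because the conservatism of the exact method absorbs it. The same holds for the pooled layout at 90% agreement and ICC 0.1. Nothing in the documents supports an ICC as high as 0.5.

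The detail may also be settled in the Independent Read Charter or the separate SAP that the protocol mentions. Neither text is in the material.

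Finally, no decision rests on the interval. No agreement threshold is set, re-reads do not enter the endpoint summaries, and the primary test, the secondary hierarchy, alpha and the sample size are untouched.

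All of this stands, and it limits the point to a conditional one of low importance. It does not remove the gap: the plan names an independence-based interval for a pooled figure without stating the condition under which that interval is valid.

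**Conclusion.** The point holds conditionally. If more than one of the three readers re-reads each selected patient, and agreement is positively correlated within a patient, the exact interval for the pooled figure is too narrow. With three re-reads, 80% agreement and ICC 0.1 to 0.5, coverage falls to about 93% to 84% with both arms pooled and about 95% to 87% by arm. The range therefore runs from no practical effect to a moderate one, and every input except the 29 per arm, the three first readers and the exact method is an assumption.

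The single-reader intervals have no repeated patients. It would go too far to call this an established error in the plan, or to say that it weakens the trial's conclusions: it concerns the precision of a descriptive reliability summary. It is worth correcting because the correction is cheap.

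**What to change.** In the image re-read paragraph of Section 12.7.1, its copy in the synopsis, and the SAP:

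1. State how many of the three first readers re-read each selected patient, and the denominator of the pooled figure, including whether it is given by arm, over both arms, or both.
2. Keep the exact 95% CI for each single reader.
3. For the pooled figure, use a patient-clustered interval when a patient contributes more than one pair: a bootstrap that resamples patients, or a GEE or ratio-estimator variance with the patient as cluster. If only one reader re-reads each patient, the exact interval can stay.
4. Note that pairs may also cluster by reader, since readers are drawn from a panel. A patient-only adjustment does not cover that, so the single-reader results should be shown beside the pooled one.

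The cost is a line or two of text, minor programming and a somewhat wider pooled interval (1.10 to 1.43 times as wide under the assumptions above). No new data are needed, and no hypothesis test or sample size changes.
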